6. ASSESSMENT AND FOLLOW-UP	9
7. STATISTICS AND DATA ANALYSIS	10
8. REGULATORY ISSUES	10
8.1 ETHICS APPROVAL	10
8.2 CONSENT	10
8.3 CONFIDENTIALITY	10
8.4 INDEMNITY	11
8.5 SPONSOR	11
8.6 FUNDING	11
8.7 AUDITS AND INSPECTIONS	11
9. STUDY MANAGEMENT	11
11. PUBLICATION POLICY	11
12. REFERENCES	11

GLOSSARY OF ABBREVIATIONS

T2DM	Type 2 Diabetes Mellitus
LRYGB	Laparoscopic Roux-en-Y Gastric Bypass
LSG	Laparoscopic Sleeve Gastrectomy
mRYGB	Mini Roux-en-Y Gastric Bypass
LAGB	Laparoscopic Adjustable Gastric Band

KEYWORDS

Obesity, Bariatric surgery, Type 2 diabetes mellitus, Gut microbiome, Metabonome

STUDY SUMMARY

TITLE Phenotyping of Bariatric Surgery Patients

DESIGN Observational study of obese patients undergoing bariatric surgery

AIMS To identify novel preoperative biomarkers of diabetes resolution following bariatric surgery

OUTCOME MEASURES HbA1c, Weight / BMI

POPULATION Obese (BMI>30kg/m²) patients undergoing bariatric surgery

ELIGIBILITY See Inclusion / Exclusion criteria

DURATION 18-month recruitment period. 2 year follow up

1. INTRODUCTION

1.1 BACKGROUND

Within the UK approximately 1 in 4 adults are now obese. This obesity epidemic is having a dramatic impact on the rise of associated chronic disease states such as type 2 diabetes mellitus (T2DM), cardiovascular disease and cancer, which in turn carry a significant global health and economic burden. The Department of Health estimates the financial cost to the NHS at £5 billion annually. Thus there is an urgent need for effective preventative and therapeutic strategies for the treatment of obesity. Disappointingly, the encouragement of lifestyle changes such as improved diet and increased exercise together with pharmacological therapies has proved largely ineffectual thus far. Hence surgical procedures have been developed to achieve more sustainable weight loss and are currently the gold standard treatment for morbid obesity. The procedures were originally designed to cause weight loss through gastric restriction and / or malabsorption. However, in addition to weight loss they have also been highly successful in the resolution of co-morbidities including diabetes, heart disease, sleep apnoea and in reducing cancer risk¹. Due to these metabolic effects they are termed 'metabolic' procedures. The metabolic outcomes are achieved through both weight-dependent and interestingly, weight-independent mechanisms^{1,2}. Indeed, many of the metabolic effects are seen before weight loss has occurred. This is because bariatric surgery induces a complex systems wide metabolic effect including disruption of the gut microbiome-host metabolic axes.

The gut microbiome has now been linked extensively with numerous disease states and it represents a novel therapeutic target in the treatment of obesity³. A low bacterial richness in the gut is associated with increased adiposity, insulin resistance and dyslipidaemia⁴. Indeed metagenome wide association studies have demonstrated the ability to identify T2DM patients based on their gut microbiome⁵. Convincingly, in an effort to establish causality, the colonisation of germ free mice with the faecal microbiota of twin pairs discordant for obesity results in significantly greater increases in body mass and adiposity in mice receiving the faecal microbiota from the obese twin⁶. However, the overwhelming disruption to the gut microbiome caused by bariatric surgery is only just being defined, as is its functional importance. This has been demonstrated in faecal transplant experiments using the gut microbiota from Roux-en-Y gastric bypass (RYGB) treated mice to transplant non-operated germ free mice, leading to significant weight loss and decreased fat mass compared to transfer of the gut microbiota from mice who had undergone sham surgery⁷. This is thought to be through mechanisms including: reduced energy harvest of non-digestible food types such as complex carbohydrates and plant polysaccharides, increased gut permeability leading to increased systemic inflammation, altered bile acid metabolism and carbohydrate fermentation products such as short-chain fatty acids acting as signalling molecules to increase satiety^{8,9}. In particular BAs have emerged as key signalling molecules, acting through the Farnesoid X Factor nuclear receptor (FXR) and G protein-coupled bile acid receptor (TGR5) to induce a number of physiological changes including; increased incretin release, improved glucose homeostasis, improved satiety, altered gut microbiota – acting in a bi-directional way, and increased metabolic rate^{10,11}. In support of this, many of the beneficial effects seen after RYGB are reproduced in rats by simply diverting bile from the common bile duct to the mid to distal jejunum via a catheter¹⁰. Additionally, following Vertical Sleeve Gastrectomy (VSG) in mice, body fat is reduced and glucose tolerance improved compared to sham-operated controls. However, body fat and glucose tolerance do not significantly differ in FXR knockout mice after VSG. Furthermore, *Bacteroides* were reduced following VSG in the wild type mice but the gut microbiota was not altered in the FXR knockout mice suggesting that FXR signalling is important in mediating the beneficial effects of VSG, in part through its modulation of the gut microbiota¹¹.

1.2 RATIONALE FOR CURRENT STUDY

From a clinical perspective, national and international guidelines for bariatric surgery have historically been based predominantly on weight. However, bariatric surgery is also highly successful in achieving remission of co-morbidities such as T2DM. The chance of remission does not appear to be weight dependent. In a recent meta-analysis T2DM remission was 72% in patients with a BMI < 35 kg/m² and 71% in patients with a BMI > 35 kg/m² undergoing bariatric surgery¹². Consequently, the latest guidelines by NICE in the UK have been updated to reflect the convincing body of evidence that surgery is also a highly successful and cost-effective treatment for T2DM patients who are less obese. As many as 2 million patients may be eligible for bariatric surgery under these new guidelines. However, unfortunately up to 30% of T2DM patients who undergo bariatric surgery do not achieve remission of their T2DM. There is currently no reliable method of identifying these patients preoperatively. T2DM remission does not appear to correlate with preoperative BMI or any other known clinical or biochemical marker reliably. Therefore novel preoperative biomarkers to help guide clinicians and policy makers select the ideal surgical candidates are urgently required to enable truly personalised healthcare.

2. STUDY OBJECTIVES

We hypothesise that weight loss and the metabolic effects of bariatric surgery are achieved in part through a functional modification of the gut microbiome and altered microbiome – host metabolome interactions. We aim to elucidate these and other mechanisms of T2DM remission following bariatric surgery. We will explore both the weight dependent and weight independent mechanisms with the translational objectives of 1) identifying novel, surgical and non-surgical, therapeutic targets and 2) identifying novel biomarkers for preoperative prognostication of T2DM remission.

3. STUDY DESIGN

Type of study: Longitudinal phenotyping of bariatric surgery patients with collection of tissue samples (blood, urine, faeces + *resected stomach from VSG patients*) and clinical data pre and postoperatively.

Duration: Patients will be followed up 2 years postoperatively. Total study time including recruitment = 60 months.

Patients: Obese patients undergoing bariatric surgery (RYGB / VSG / mRYGB / LAGB).

3.1 STUDY OUTCOME MEASURES

The 1^o clinical outcome measure will be diabetes remission defined as HbA1c < 42 mmol/mol. The 2^o clinical outcomes will be partial diabetes remission (HbA1c < 48 mmol/mol), HbA1c reduction and % excess weight loss.

These clinical outcomes will be mapped to metabolomic and metagenomic data to identify preoperative markers of diabetes remission and weight loss.

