4.2 INCLUSION CRITERIA

Referred to the Imperial Weight Centre (NHS) Tier 4 service team for consideration bariatric surgery (RYGB / VSG / mRYGB / LAGB), Obese (BMI>30kg/m²), Age ≥18, failure of efforts at lifestyle modification and dieting, fitness for anaesthesia and procedure, willingness to comply with the trial protocol.

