6. ASSESSMENT AND FOLLOW-UP

Patients will undergo follow up according to the usual bariatric surgery follow up protocol at the Imperial Weight Centre.

- At patients usual preoperative, 3 month, 1 and 2 year postoperative outpatient appointments patients will provide additional samples of blood, urine and faeces for analysis.
- Patients will be given brief online 24-hour diet recall questionnaires to complete while waiting for their usual outpatient appointments. They will then be asked to complete entries for two days following each hospital visit using a personal computer via a personal link to a secure website provided.
- Patients will be sent home with 24-hour urine collection bottles. They will be asked to provide 24-hour collections for before surgery and the days before their 3-month and 1-year outpatient visits. They will be able to return their samples when they attend these appointments.
- At the time of surgery researchers will collect resected stomach tissue from LSG patients that would usually be disposed.
- Clinical data will be retrieved from the medical notes preoperatively to 2 years postoperatively.

Study End: 130 type 2 diabetic and 65 non-diabetic patients will be recruited and followed-up until 2 years postoperatively.

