7. STATISTICS AND DATA ANALYSIS

Multivariate statistical analysis will be performed on the generated metabonomic and metagenomic data sets. This will include unsupervised principal components analysis (PCA) and supervised partial least squares discriminant analysis with orthogonal signal correction (OPLS-DA) and O2-PLS between data sets. Mapping T2DM outcomes to metabonomic and metagenomic data will potentially identify novel preoperative biomarkers that are able to prognosticate T2DM resolution following bariatric surgery.

Due to the complexity of metabonomic data sample size calculations are difficult and there is currently no standardised technique. We used peer-reviewed MetSizeR methodology to calculate appropriate sample sizes¹³. Using principal component analysis on an expected metabonomic data set of 300 metabolites of which 20% differentiate significantly and a targeted false discovery rate of 5%, over 15 samples are needed in each group.

Approximately 30% of obese diabetic patients do not have resolution of disease following bariatric surgery¹². To allow for an expected drop out rate of 20% at 1 year we will recruit 65 patients undergoing RYGB and 65 patients undergoing VSG to achieve 15 patients with non-resolution of diabetes and 36 patients with resolution in each surgical group. We will also aim to recruit 65 non-diabetic patients undergoing surgery to act as a control group. This will enable comparison against diabetic patients that undergo remission after surgery.

Four surgeons at the Imperial Weight Centre collectively perform approximately 220 RYGB and 180 VSG procedures a year. In previous years 25% of patients have had T2DM. However, we expect this percentage to rise since the introduction of new NICE guidelines encouraging bariatric surgery in diabetic patients in November 2014. We expect to recruit 1-2 patients a week that meet the inclusion criteria and have completed recruitment after 18 months.

Data and all appropriate documentation will be stored for a minimum of 10 years after the completion of the study, including the follow-up period.

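### Diabetes remission is defined by HbA1c alone, so a patient whose HbA1c is controlled by drugs is labelled a remission

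*Combined protocol and SAP*

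**What the plan says.** Section 3.1 states that the primary "clinical outcome measure will be diabetes remission defined as HbA1c < 42 mmol/mol". The secondary outcomes are "partial diabetes remission (HbA1c < 48 mmol/mol), HbA1c reduction and % excess weight loss". Those thresholds are the whole definition. The Study Summary line reads "OUTCOME MEASURES HbA1c, Weight / BMI" and has no medication measure.

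The inclusion criteria (4.2) cover referral, BMI and age, and end with "failure of efforts at lifestyle modification and dieting, fitness for anaesthesia and procedure, willingness to comply with the trial protocol". The exclusion criteria (4.3) concern previous surgery, pregnancy and capacity. Neither list limits HbA1c or medication at entry.

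On data collection, section 6 says "Clinical data will be retrieved from the medical notes preoperatively to 2 years postoperatively", without listing the items.

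Section 2 gives as one translational objective "identifying novel biomarkers for preoperative prognostication of T2DM remission". Sections 3.1 and 7 map the clinical outcome to the metabonomic and metagenomic data, including by supervised OPLS-DA. Section 7 also compares diabetic patients who remit with 65 non-diabetic controls. Its group sizes start from "Approximately 30% of obese diabetic patients do not have resolution of disease following bariatric surgery", with no statement of how resolution is defined there.

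**The concern.** The protocol treats remission as something that surgery brings about, and it lists HbA1c reduction as a separate outcome. Remission is therefore meant to be more than a glucose level. An HbA1c below 42 mmol/mol in a patient taking glucose-lowering drugs does not show that the diabetes has resolved, yet the stated rule counts it as remission. In the clearest case, a treated patient enters below 42, stays on the same drugs, is still below 42 after surgery, and is labelled a remission although nothing has changed.

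The label matters because a supervised analysis learns whatever separates the classes it is given. If the remission class mixes patients in remission with patients under drug control, a preoperative marker may predict good HbA1c control instead. The comparison with non-diabetic controls is affected in the same way, because some of the remitters would be people with treated diabetes. A larger sample does not remove a labelling error of this kind.

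**Working it through.** **1. Is a drug condition stated anywhere?** I compared the Study Summary, sections 1.2, 2 and 3.1, eligibility (4.2, 4.3), follow-up (6) and statistics (7). None mentions diabetes drugs as part of the outcome, a period off drugs, or the recording of medication. The rule is complete as written and does not use drug treatment.

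**2. The plan's own counts (section 7, per surgical group).** Inputs: 65 recruited, 20% dropout at 1 year, 30% non-resolution.

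- Evaluable: 65 × (1 − 0.20) = 52
- Non-resolution: 52 × 0.30 = 15.6 (plan: 15)
- Resolution: 52 × 0.70 = 36.4 (plan: 36)

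The plan's figures reproduce.

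**3. How many labels could be wrong?** The documents give no rate of postoperative drug use, so the share m of labelled remitters who are on drugs is assumed at 10%, 20% and 30%. Suppose the 30% rate is based on HbA1c alone at the 42 threshold. The number mislabelled is 36.4 × m. An off-drug label moves these patients to the non-remission class.

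| m | Mislabelled | Remission, off-drug label | Non-remission, off-drug label |
|---|---|---|---|
| 10% | 3.6 | 32.8 | 19.2 |
| 20% | 7.3 | 29.1 | 22.9 |
| 30% | 10.9 | 25.5 | 26.5 |

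Both classes stay above 15 throughout.

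**4. The other basis for the 30% rate.** Suppose instead that the rate already counts drug-treated patients as non-resolved, and that a share p of the 15.6 reaches HbA1c below 42 on drugs. The written rule then moves 15.6 × p of them into remission. For p = 10%, 20% and 30% that is 1.6, 3.1 and 4.7 patients, leaving 14.0, 12.5 and 10.9 labelled non-remitters. The documents do not say which basis applies. If the cited rate used another HbA1c threshold, neither set of counts applies.

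**5. Effect on the class difference (basis of step 3).** Let the true mean marker levels be μR in remission and μN in non-remission.

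- *Drug-controlled patients resemble non-remitters.* The labelled remission mean is (1 − m)μR + mμN, so the difference is (1 − m)(μR − μN). It falls to 90%, 80% or 70% of its true size, and the off-drug label restores it.
- *Drug-controlled patients lie halfway between the classes.* The written label loses m/2 of the difference. The off-drug label puts the same patients into the other class and loses ½ × 36.4m / (15.6 + 36.4m). The second loss is larger whenever 36.4 > 15.6 + 36.4m, that is, whenever m < 20.8/36.4 = 0.57. This covers the whole assumed range, so the off-drug label gives no gain in contrast here.

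**The case against.** The strongest reply accepts the text and disputes the consequences.

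First, an off-drug label has its own error. Follow-up is usual care, so a patient still prescribed a drug that is no longer needed would be labelled a non-remitter. This stands. It is a reason to report both labels, but it does not make the HbA1c-only rule a measure of remission.

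Second, no figure in the documents sizes the problem. This also stands, and it rules out two stronger readings that a reader might infer. One is that the written rule weakens the biomarker contrast and that the fix would restore power. That holds if drug-controlled patients resemble non-remitters but not if they lie halfway, and the documents do not say where they lie. The other is that the rule pushes the non-remission group below the 15 planned. That occurs only on the basis in step 4 of the working; on the basis in step 3 the written rule costs nothing against that target.

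Third, a reader might infer from section 6 that medication will not be collected. The section does not support that: its general reference to clinical data does not name HbA1c either, although HbA1c is the primary outcome. Medication may well be in the notes. What can be said is that the stated label does not use it.

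Fourth, the study is observational, with an exploratory multivariate analysis, and no treatment, visit or sample depends on the label. The definition can therefore be corrected later. This lowers the urgency. It does not remove the need to settle the rule before outcomes are examined, since otherwise the label could be chosen after the data are seen.

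**Conclusion.** The point holds as one of label validity. Followed exactly, section 3.1 labels drug-controlled diabetes as remission, including in patients already below the threshold before surgery. A marker found with that label could not be presented as a marker of remission. This conclusion rests on the text alone.

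The size is unknown. The range of 3.6 to 10.9 mislabelled patients out of 36.4 per surgical group rests on assumed drug-use shares of 10% to 30% and on the 30% rate being HbA1c-only at 42. A fall in the class difference to between 90% and 70% needs the further assumption that these patients resemble non-remitters. Neither lost power nor a shortfall in the non-remission group is established.

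This should be fixed, but it does not put the study at risk: provided that medication is recorded in the notes, it can be corrected before analysis without losing data.

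**What to change.** - **Section 3.1.** For outcome labelling, define remission and partial remission as HbA1c below the stated threshold with no glucose-lowering medication at the time of that HbA1c, at one named postoperative visit. One year would match the dropout basis in section 7. Whether a minimum period off medication is required, and how long, is for the investigators to state.
- **Section 6.** Name glucose-lowering medication, at baseline and at each visit, as an item extracted from the notes.
- **Analysis.** Report the HbA1c-only label as a sensitivity analysis, and flag patients whose preoperative HbA1c was already below the threshold.
- **Section 7.** State which definition of resolution, both threshold and drug condition, the 30% rate uses.

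This changes how outcomes are labelled and does not affect treatment. The cost is a few sentences and one more item taken from notes already being retrieved, with no new visits, samples or recruits. The drawbacks are a lower remission rate and a label that depends partly on usual-care prescribing; the sensitivity analysis shows how far the results depend on the choice of label.

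### HbA1c reduction and % excess weight loss both contain the preoperative value, but the plan names no baseline adjustment when searching preoperative omics data for markers of them

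*Combined protocol and SAP*

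**What the plan says.** Section 3.1 defines the primary outcome as remission on an HbA1c threshold. The secondary outcomes are partial remission, "HbA1c reduction and % excess weight loss". It gives no formula, baseline visit or excess-weight reference for the last two. It then states their use: "These clinical outcomes will be mapped to metabolomic and metagenomic data to identify preoperative markers of diabetes remission and weight loss".

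Section 7 is the only statistics section. After PCA it lists "supervised partial least squares discriminant analysis with orthogonal signal correction (OPLS-DA) and O2-PLS between data sets". The list is introduced as what the analysis will include, so it is not closed. No covariate is named anywhere: no preoperative HbA1c, weight or BMI.

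The data for such a term will exist. Section 6 says: "Clinical data will be retrieved from the medical notes preoperatively to 2 years postoperatively".

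**The concern.** In ordinary usage, HbA1c reduction is the preoperative value minus the postoperative value, and % excess weight loss is weight lost divided by preoperative excess weight. The preoperative measurement therefore sits inside each outcome.

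A preoperative metabolite that carries only the information already in preoperative HbA1c will tend to correlate with HbA1c reduction, through the arithmetic of the outcome. A metabolite that only reflects BMI may correlate with % excess weight loss through the denominator.

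The study wants novel markers because, according to Section 1.2, existing ones do not serve. A hit that restates a number already in the notes does not meet that aim, and the plan has no stated step that would reveal it. If adjustment is left open, it could also be decided after the results are seen.

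**Working it through.** **The plan's own figures.** Section 7 recruits 65 diabetic patients per procedure and allows 20% dropout: 65 × 0.80 = 52. With 30% non-resolution, 52 × 0.30 = 15.6 and 52 × 0.70 = 36.4. This agrees with the plan's aim "to achieve 15 patients with non-resolution of diabetes and 36 patients with resolution in each surgical group". So n = 52 per procedure, or 130 × 0.80 = 104 with both procedures pooled.

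**Assumed inputs (none are in the documents).** k is the post/pre SD ratio of HbA1c, 0.5 to 1. ρ is the pre-post correlation, 0 to 0.6. r is the correlation of a metabolite with preoperative HbA1c, 0.5 (also 0.3). The metabolite has no effect of its own. Single-metabolite tests are used as an illustration; they are not the planned multivariate methods.

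**HbA1c reduction.**

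corr(baseline, reduction) = (1 − kρ) / √(1 + k² − 2kρ)

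- k = 0.5, ρ = 0: 1/√1.25 = 0.89. Induced correlation of the proxy: 0.5 × 0.89 = 0.45.
- k = 1, ρ = 0.6: 0.4/√0.8 = 0.45. Induced correlation: 0.5 × 0.45 = 0.22.

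Simulated rates at which this uninformative proxy is flagged at n = 52, over k = 0.5 to 1 and ρ = 0 to 0.6:

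| Proxy | p < 0.05 | p < 0.05/300 |
|---|---|---|
| r = 0.5 | 36-93% | about 1-32% |
| r = 0.3 | 16-49% | about 0.2-3% |

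The second column is the strictest bound for the 300 metabolites that Section 7 assumes. A 5% false-discovery procedure, the target in Section 7, would lie between the columns. If ρ runs to 0.9, the first cell widens to 12-95%. At n = 104, r = 0.5 and ρ up to 0.6, the rate at p < 0.05 is 63-99.8%.

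**After adjustment for preoperative HbA1c, at p < 0.05.** The rate is 4.7-5.3%, but only because the proxy was made to track the recorded value. If it tracks underlying glycaemia and recorded HbA1c has reliability 0.8 (assumed), the adjusted rate is about 5-15% at n = 52 and reaches about 26% at n = 104, for correlations between underlying pre and post glycaemia up to 0.9.

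**% excess weight loss.** With an assumed reference BMI of 25:

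% EWL = % weight loss × BMI / (BMI − 25)

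For the same 28% weight loss (assumed), BMI 35 gives 28 × 35/10 = 98% and BMI 46 gives 28 × 46/21 = 61%. If heavier patients lose proportionally more, the two effects offset. Simulation at n = 52, with a BMI proxy of r = 0.5, p < 0.05, mean BMI 42 or 46 (SD 5 or 8) and % weight loss SD 8 or 10:

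| corr(% weight loss, BMI) | Flagged |
|---|---|
| −0.3 | 58-78% |
| 0 | 27-63% |
| +0.3 | 7-43% |
| +0.4 | 6-35% |

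After adjustment for BMI the rate is 4.3-5.7% throughout.

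**Whether the named methods remove this.** Orthogonal signal correction strips omics variation that is unrelated to the outcome. Baseline-driven variation is related to these outcomes, so it stays. With a single outcome y, the predictive (O)PLS weight is proportional to X′y, that is, to each autoscaled metabolite's correlation with y, so the induced correlation carries through.

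**The case against.** The strongest reply is that this criticises a model the plan does not write down. OPLS-DA classifies groups, O2-PLS links data sets, and no regression of either continuous outcome is described. Section 7 speaks of mapping diabetes outcomes, and Section 3.1 names remission and weight loss as the targets of the marker search, not HbA1c reduction. The two outcomes are not even defined by formula. This stands in part: that they contain the preoperative value is an inference from ordinary meaning, and no specific model is named for them. But Section 3.1 sends all the listed clinical outcomes into the mapping, and % excess weight loss is the only weight-loss outcome it lists.

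Second, the size is set by assumption. This stands. The ranges are wide, the p<0.05 figures are lenient beside a false-discovery target, and the % excess weight loss effect comes close to the nominal 5% in some settings. They show that the mechanism can matter, not how much it will.

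Third, the method list is open and the baseline data are retrieved, so adjustment remains possible. True; the gap is only that it is not prespecified.

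Fourth, a marker that acts through baseline glycaemia or BMI may still predict. Also true, and a reason to show both analyses rather than replace one with the other.

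A reader might go further and infer that the primary outcome is compromised. The documents do not support that. Remission is a threshold on the postoperative value, not a change from baseline. It would be affected only if preoperative HbA1c predicts remission, and Section 1.2 says: "T2DM remission does not appear to correlate with preoperative BMI or any other known clinical or biochemical marker reliably". That sentence concerns remission, so it does not answer the point for the two secondary outcomes.

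**Conclusion.** The point holds for two secondary outcomes of an exploratory observational study. For HbA1c reduction the induced association is positive in every case examined (baseline-reduction correlation 0.22 to 0.93, with ρ up to 0.9). For % excess weight loss it is possible but depends on how % weight loss varies with BMI, and it can nearly vanish. Every percentage rests on assumed SD ratios and correlations and on single-metabolite tests.

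Three stronger readings should be resisted, besides the one about remission. The sample size is not called into question: its arithmetic reproduces and it does not depend on these outcomes. Nor should the effect be sized on all recruits less dropout, (130 + 65) × 0.80 = 156. Section 7 describes the 65 non-diabetic patients as a control group for comparison with remitters and sets out no pooled weight-loss analysis. Finally, adjustment should not be taken as a complete cure, because measurement error in HbA1c leaves some of the association in place.

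This is a cheap improvement that the sponsor could make.

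**What to change.** In Section 7, keep the declared outcomes and add text to this effect:

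*For HbA1c reduction and % excess weight loss, the outcome and each omics variable will be residualised on preoperative HbA1c or preoperative BMI respectively before (O)PLS, or that value will be entered as a covariate in per-feature models. Unadjusted and adjusted results will be shown side by side. A marker will be called novel only if it remains after adjustment.*

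The formula for each outcome, with its baseline visit and excess-weight reference, should be stated in the same place, since the adjustment depends on it.

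The cost is a few lines of analysis text. No new visit, sample or patient is needed. The downsides are fewer nominal hits and the risk of masking a marker that acts through baseline glycaemia or BMI; showing both results addresses the second.
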